In parallel, untargeted metabolomics profiling panels will be applied as an unbiased screening for the relative concentrations of metabolites. These analyses will be subcontracted to Metabolon, an internationally renowned metabolomics service company who provides high sensitivity analyses of more than 1000 metabolites. The principal investigator has previous experience with Metabolon data from a diet-exercise study.³¹ Samples will be analysed using ultra-high-performance liquid chromatography-tandem mass-spectrometry (UPLC-MS/MS; positive mode), UPLC-MS/MS (negative mode) and gas chromatography-MS (GC-MS).⁵⁶ The Metabolon platform combines multiple MS methods and a laboratory information managements system with the industry's largest reference library of authenticated metabolite standards and has a suite of patented informatics and quality-control software. These features collectively allow us to overcome the 'signal-to-noise' challenges of other metabolomics platforms. In addition to the global metabolomics profiling, we will undertake Complex Lipid Panel profiling at Metabolon. Complex lipids are a diverse class of metabolites that play important roles in the development of metabolic diseases and inflammation. Because these metabolites have a diverse array of chemical structures and a high degree of isomeric overlap, lipids are exceptionally challenging to accurately identify and quantify. The Complex Lipid Panel, developed by Metabolon, is currently the best (and only) lipidomic platform to provide complete speciation data. The Complex Lipid Panel identifies up to 1,100 individual lipid species, offering unparalleled insight into the lipidome.

Cytokine and hormone profiling

We will measure a network of 27 cytokines of relevance for inflammatory status⁵⁷ (Human Cytokine Group I multiplex panel) using Luminex xMAP Technology on a Bio-Plex 200 system (Bio-Rad) at the Cellular and Molecular Imaging Core Facility (CMIC), NTNU. Since subclinical mastitis, which is a common condition, induces substantial changes in inflammatory breastmilk components⁵⁸, information of mastitis prevalence will be recorded and adjusted for in the statistical analyses. Breastmilk insulin, leptin, adiponectin will be measured by enzyme-linked immunosorbent assays (ELISA) using DS2 ELISA processing system (Dynex Technologies) at the Dept. of Circulation and Medical Imaging.

Micro-RNA sequencing

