Acute Effects of Endurance Exercise with Moderate and High Intensity on Breast Milk Composition Among Women with Overweight/Obesity

Acronym: YT

NCT number: NCT05745922

Document date: 07. September 2025

Statistical Analysis Plan

Study design: Randomized crossover study

Aim: Determine the effect of moderate-intensity continuous training and high-intensity interval training on human milk concentrations of metabolites, lipids, cytokines, hormones and miRNAs in lactating women with overweight/obesity.

Overview:

- Up to N=30 women with $\text{BMI} > 25 \text{ kg/m}^2$
- Each participant goes through three conditions in random order (six possible sequences) and has milk sampled at four time points per condition (one pre-condition and three post-condition).
- Washout period: 1 week between conditions
- The samples are analysed for a range of outcome variables within different molecular data ('omics') categories.

Conditions:

- C1: No exercise, resting in the lab
C2: Moderate-intensity continuous training
C3: High-intensity interval training

Time points:

- T1: 7 am (pre-condition)
T2: 11 am (immediately after condition)
T3: 12 am (1-hour post-condition)
T4: 15 am (4 hours post-condition)

Pre-planned outcome groups measured in human milk:

- Targeted NMR metabolomics (GCF)
Metabolomics + lipidomics profile panels (Metabolon)
Cytokines (Olink)
Hormones (insulin, ghrelin, leptin, adiponectin, IGF-1)
miRNA (GCF)

Statistical analysis plan

For each outcome category, the primary objective is to evaluate the effect of conditions C2 and C3 on the outcome variables at time points T2, T3, and T4, using condition C1 and time point T1 as references. Outcomes measured in all participants will be analysed according to the intention-to-treat principle, whereas outcomes measured only in participants who followed the protocol perfectly will be analysed according to the per-protocol principle. The decision whether to include all samples or only those from participants who complied with the protocol will depend on the costs of including the extra (non-compliant) samples for each outcome group.

We will perform the following six analysis steps for all outcome groups:

1) Data preparation (batch adjustment, log transformation, imputation)

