- If needed, the outcome data will be batch adjusted, imputed (e.g. using the R package *zCompositions*), and log transformed appropriately before analysis. Adjustments and transformations will depend on whether the data is already normally distributed, and if it is required for the method in question.
- The metabolomics data from Metabolon already comes in a log-transformed, batch-normalized version where missing values (below the detection limit) are imputed to the observed minimum for that metabolite after batch normalization. These will be used in all analyses.

2) Principal component analysis (PCA)

- We will use PCA to detect outliers and identify global structures/important features by capturing the maximum variance in the dataset, and test if the data separates according to the conditions in an unsupervised setting.
- We will identify the number of PCs that explain 95% of the variation in the data at baseline, for use in multiple testing adjustment.

3) Linear mixed model (LMM) analyses:

- We will use LMM analyses to evaluate the effects of each condition and time point on all outcome variables:
- We will analyse the effects of time and time-condition interaction as fixed effects, and participant ID as a random intercept (Eq 1). The analysis will be reference coded, with C1 (no exercise) and T1 (morning) as reference points. We will not adjust for or subtract baseline values in the model.

Eq. 1: $\text{value} \sim \text{time} + \text{time:condition} + (1|\text{id})$

- We will run the LMM analyses using e.g. the lme4 R package, and estimate p-values using the Satterthwaite method, e.g., as implemented in the lmerTests R package.
- Multiple testing correction: We will use a multiple testing corrected p-value threshold determined by dividing the alpha level (0.05) by the number of PCs explaining 95% of the variation in the outcome data at baseline.
- For variables passing the multiple testing corrected p-value cut-off, we will test for potential carry-over effects by adjusting for sequence (Eq. 2) in sensitivity analysis:

Eq. 2: response matrix ~ time + time:condition + sequence + sequence:condition + time:sequencec:condition + (1|id)

4) Repeated Measures (RM)-ASCA+

- We will use RM-ASCA+ to evaluate the overall effect of each condition and time point on each outcome data category. We will model all variables within the same data category together in a multiple-response variable analysis.

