- We will analyse both the combined and separate effects of time and time-condition interaction as fixed effects, and participant ID as a random intercept (Eq 3). The analysis will be reference coded, with C1 (No exercise) and T1 (morning) as reference points. We will not adjust for or subtract baseline values in the model.

Eq. 3: response matrix ~ time + time:condition + (1|id)

- Each variable will be scaled by the standard deviation of the baseline (morning) samples across conditions.
- We will use cluster bootstrapping with 1000 iterations to validate the findings and generate confidence intervals.

The results from the LMM and RM-ASCA+ analyses will guide follow-up analyses using additional machine learning models (PLS-DA, t-SNE).

5) Partial Least Squares Discriminant Analysis (PLS-DA)

- Supervised machine learning approach to analyse differences between the conditions. We will provide the model with a response matrix specifying the conditions, and the model will maximize separation between the conditions. The

method works well with small datasets and multiclass scenarios (here: multiple conditions).

- We will use PLS-DA for feature selection/to explore global structures in the data or find variables that are especially important for one time/condition compared to another. The LMM and RM-ASCA+ analyses will guide the selection of conditions/time points for comparison.
- We will perform cross-validation and permutation testing with 1000 repetitions.

6) T-Distributed Stochastic Neighbour Embedding (t-SNE)

- We will use t-SNE in an exploratory analysis to look for clusters of variables by preserving local relationships (pairwise similarities between data points, clusters).

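### The protocol commits to adjusting for mastitis, but no SAP model or step includes it; where status changes between a woman's visits, the cytokine contrasts lose precision

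*Protocol*

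**What the plan says.** The protocol, under Cytokine and hormone profiling, gives both a reason and a commitment. The reason is that "subclinical mastitis, which is a common condition, induces substantial changes in inflammatory breastmilk components". The commitment is that "information of mastitis prevalence will be recorded and adjusted for in the statistical analyses".

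The SAP carries a later date and puts every outcome group, cytokines included, through the same six steps.

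- **Step 3 (mixed model, Eq. 1):** "We will analyse the effects of time and time-condition interaction as fixed effects, and participant ID as a random intercept (Eq 1").
- **Step 3 (carry-over sensitivity analysis, Eq. 2):** the terms are "time + time:condition + sequence + sequence:condition + time:sequencec:condition + (1|id"), so only sequence terms are added.
- **Step 4 (RM-ASCA+, Eq. 3):** "response matrix ~ time + time:condition + (1|id").
- **Baseline, in both steps:** "We will not adjust for or subtract baseline values in the model".

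Data preparation, PCA, PLS-DA and t-SNE name no mastitis covariate, exclusion or sensitivity analysis. Mastitis is not among the exclusion criteria in the protocol's Experimental design section.

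**The concern.** The two documents disagree on a named adjustment, and neither says that the commitment was withdrawn. The affected outcomes are the ones for which the protocol itself gives the reason: inflammatory milk components.

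The SAP's aim is to "evaluate the effect of conditions C2 and C3 on the outcome variables at time points T2, T3, and T4", with C1 and T1 as references. Each condition is a separate visit, one week from the next. A woman with mastitis at one visit and not at another has all her values for one condition shifted relative to the others. A participant intercept removes only what is common to her three visits. Eq. 1 has no visit effect, and the same-day morning sample, which could cancel a shift lasting the whole visit, is not used for that purpose. The shift then stays in the C2-versus-C1 and C3-versus-C1 contrasts as extra variance. If the choice to adjust is left open until results are known, it also becomes a post hoc choice.

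**Working it through.** **What the documents supply.** At least 20 women with complete data (Protocol, Participants) and up to 30 (SAP, Overview); one week between conditions; a threshold of 0.05 divided by the number of components explaining 95% of baseline variation, a number not given. The protocol declines a power calculation, so there is no planned figure to reproduce.

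**What has to be assumed.** Share of visits affected, p: 5% to 20%. Shift while affected, d: 1 to 3 residual SDs, lasting the whole visit. Correlation of status between a woman's visits, r: 0 to 1. Number of components: 15, varied below. The benchmark is the effect that 20 women would detect with 80% power if there were no mastitis.

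**Step 1: does the shift reach the contrast?** In a noise-free fit of the three-condition, four-time design, suppose k of N women are affected only at the C3 visit. The C3-versus-C1 contrasts at T2, T3 and T4 each move by k × d / N. For one woman that is 0.05d at N = 20 and 0.033d at N = 30. The result is the same whether the T1 condition terms are free or set to zero.

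**Step 2: variance.** The variance of a between-visit contrast is multiplied by 1 + p(1 − p)(1 − r)d².

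**Step 3: power.** For a paired comparison with n = 20 and two-sided alpha 0.05/15 = 0.0033, the noncentral t distribution gives 80% power at a standardised paired effect of 0.954, a noncentrality of 0.954 × √20 = 4.27. Dividing by the square root of the variance ratio gives the new noncentrality. For a ratio of 1.36 it is 4.27/√1.36 = 3.66, and power is 62%.

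| Visits affected | Shift (SD) | r | Variance ratio | Power |
|---|---|---|---|---|
| 5% | 1 | 0 | 1 + 0.0475 × 1 = 1.05 | 78% |
| 10% | 2 | 0 | 1 + 0.09 × 4 = 1.36 | 62% |
| 10% | 2 | 0.5 | 1 + 0.09 × 0.5 × 4 = 1.18 | 71% |
| 10% | 2 | 0.8 | 1 + 0.09 × 0.2 × 4 = 1.07 | 76% |
| 10% | 2 | 1 | 1.00 | 80% |
| 20% | 3 | 0 | 1 + 0.16 × 9 = 2.44 | 31% |

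At a ratio of 1.36, 20 women carry the information of 20/1.36 = 14.7. The number of components matters little: in the 10%, 2 SD, r = 0 case, power runs from 67% with 1 component to 61% with 25.

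**Step 4: simulation of the crossover** (N = 20, independent visits, 1,500 runs per setting). Mean bias is about zero. The standard error of the C3-versus-C1 contrast at T2 rises from 0.316 to about 0.37 residual SD (10%, 2 SD) and 0.50 (20%, 3 SD). Nominal 5% type I error is about 5 to 6% and 8% in those two settings. With a visit-level covariate the standard error returns to 0.30 to 0.33 and type I error to about 0.04 to 0.06. If status is constant across a woman's visits, the standard error without the covariate is already 0.32 to 0.33.

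**The case against.** Nobody can argue that the adjustment is present; the objections concern its consequence.

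**Persistence.** Milk comes from the same breast throughout, and the visits fall within a few weeks. A status that lasts over all three is an additive shift that the intercept absorbs. A reader might infer that the protocol describes a disturbance that changes from visit to visit. It does not: it calls the condition common and its effect substantial, and says nothing about visits. Change between visits is an inference from the one-week spacing. This objection stands, and it is why the size is shown over r. The 62% figure is the worst case among non-negative correlations for that prevalence and shift.

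**Bias.** A reader might also infer that omitting the term biases the comparison of conditions. With randomised order the expected bias is zero. Chance imbalance does occur: with 10% of visits affected independently and 20 women, two conditions differ by two or more affected visits 42% of the time. But that is the same effect that the larger standard error measures, not an additional harm. A net difference of two visits at 2 SDs moves the contrast by 2 × 2/20 = 0.2 SD, less than one standard error (√(2/20) = 0.32).

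**T1 as reference.** T1 is a reference level in the model, which might seem to remove a shift lasting all day. It would do so only if the contrast were formed as a change from that visit's own T1. Step 1 of the check shows that the condition contrasts at T2 to T4 keep the shift, and the SAP rules out subtracting baseline.

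**Exploratory aim.** The protocol cites the exploratory nature of the research and sets no power target, so the 80% benchmark is this review's own. That limits the weight of the power figures but does not reconcile the two documents.

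**Conclusion.** The mismatch is certain and needs no assumption: the protocol promises a mastitis adjustment and the SAP contains none. The consequence is a possible loss of precision for inflammatory markers, with at most mild type I inflation in the settings simulated. For independent visits, power against an 80% benchmark ranges from 78% (5% of visits, 1 SD) to 31% (20%, 3 SD). With 10% of visits and a 2 SD shift it is 62% if visits are independent, 71% at correlation 0.5 and unchanged at correlation 1. Prevalence, shift, correlation and the 15 components are all assumed; the documents give none of them.

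Two further readings go beyond the text. One is that the data needed are already in hand. The protocol says that mastitis will be recorded, but not when, how often, for which breast or how subclinical cases are detected, and its Questionnaires section does not list it. The other is that hormones need the same term. The sentence sits under a heading that covers both, but its stated reason concerns inflammatory components only. The change should be made, because the commitment exists and meeting it is cheap if the data allow.

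**What to change.** 1. Define mastitis status in the SAP: how it is ascertained, when, and that it refers to the sampled breast.
2. Where status was recorded at each visit, add it as a fixed covariate to Eq. 1 and Eq. 3 for the cytokine outcomes. Extending it to hormones would need its own stated reason.
3. Add a sensitivity analysis for the same outcomes that drops affected visits.
4. If status was recorded only once per woman, or the adjustment has been abandoned, amend the documents to say so and why. A once-only record would add little beyond the participant intercept.

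The cost is one extra parameter per model and a few lines of SAP text if per-visit status exists. The documents do not confirm that it does; if it does not, either data collection changes or the protocol's commitment has to be amended. The choice should be fixed before the cytokine results are seen.

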Acute Effects of Endurance Exercise with Moderate and High Intensity on Breast Milk Composition Among Women with Overweight/Obesity

Acronym: YT

NCT number: NCT05745922

Document date: 07. September 2025

Statistical Analysis Plan

Study design: Randomized crossover study

Aim: Determine the effect of moderate-intensity continuous training and high-intensity interval training on human milk concentrations of metabolites, lipids, cytokines, hormones and miRNAs in lactating women with overweight/obesity.

Overview:

- Up to N=30 women with $\text{BMI} > 25 \text{ kg/m}^2$
- Each participant goes through three conditions in random order (six possible sequences) and has milk sampled at four time points per condition (one pre-condition and three post-condition).
- Washout period: 1 week between conditions
- The samples are analysed for a range of outcome variables within different molecular data ('omics') categories.

Conditions:

- C1: No exercise, resting in the lab
C2: Moderate-intensity continuous training
C3: High-intensity interval training

Time points:

- T1: 7 am (pre-condition)
T2: 11 am (immediately after condition)
T3: 12 am (1-hour post-condition)
T4: 15 am (4 hours post-condition)

Pre-planned outcome groups measured in human milk:

- Targeted NMR metabolomics (GCF)
Metabolomics + lipidomics profile panels (Metabolon)
Cytokines (Olink)
Hormones (insulin, ghrelin, leptin, adiponectin, IGF-1)
miRNA (GCF)

Statistical analysis plan

For each outcome category, the primary objective is to evaluate the effect of conditions C2 and C3 on the outcome variables at time points T2, T3, and T4, using condition C1 and time point T1 as references. Outcomes measured in all participants will be analysed according to the intention-to-treat principle, whereas outcomes measured only in participants who followed the protocol perfectly will be analysed according to the per-protocol principle. The decision whether to include all samples or only those from participants who complied with the protocol will depend on the costs of including the extra (non-compliant) samples for each outcome group.

We will perform the following six analysis steps for all outcome groups:

1) Data preparation (batch adjustment, log transformation, imputation)

- If needed, the outcome data will be batch adjusted, imputed (e.g. using the R package *zCompositions*), and log transformed appropriately before analysis. Adjustments and transformations will depend on whether the data is already normally distributed, and if it is required for the method in question.
- The metabolomics data from Metabolon already comes in a log-transformed, batch-normalized version where missing values (below the detection limit) are imputed to the observed minimum for that metabolite after batch normalization. These will be used in all analyses.

2) Principal component analysis (PCA)

- We will use PCA to detect outliers and identify global structures/important features by capturing the maximum variance in the dataset, and test if the data separates according to the conditions in an unsupervised setting.
- We will identify the number of PCs that explain 95% of the variation in the data at baseline, for use in multiple testing adjustment.

3) Linear mixed model (LMM) analyses:

- We will use LMM analyses to evaluate the effects of each condition and time point on all outcome variables:
- We will analyse the effects of time and time-condition interaction as fixed effects, and participant ID as a random intercept (Eq 1). The analysis will be reference coded, with C1 (no exercise) and T1 (morning) as reference points. We will not adjust for or subtract baseline values in the model.

Eq. 1: $\text{value} \sim \text{time} + \text{time:condition} + (1|\text{id})$

- We will run the LMM analyses using e.g. the lme4 R package, and estimate p-values using the Satterthwaite method, e.g., as implemented in the lmerTests R package.
- Multiple testing correction: We will use a multiple testing corrected p-value threshold determined by dividing the alpha level (0.05) by the number of PCs explaining 95% of the variation in the outcome data at baseline.
- For variables passing the multiple testing corrected p-value cut-off, we will test for potential carry-over effects by adjusting for sequence (Eq. 2) in sensitivity analysis:

Eq. 2: response matrix ~ time + time:condition + sequence + sequence:condition + time:sequencec:condition + (1|id)

4) Repeated Measures (RM)-ASCA+

- We will use RM-ASCA+ to evaluate the overall effect of each condition and time point on each outcome data category. We will model all variables within the same data category together in a multiple-response variable analysis.
- We will analyse both the combined and separate effects of time and time-condition interaction as fixed effects, and participant ID as a random intercept (Eq 3). The analysis will be reference coded, with C1 (No exercise) and T1 (morning) as reference points. We will not adjust for or subtract baseline values in the model.

Eq. 3: response matrix ~ time + time:condition + (1|id)

- Each variable will be scaled by the standard deviation of the baseline (morning) samples across conditions.
- We will use cluster bootstrapping with 1000 iterations to validate the findings and generate confidence intervals.

The results from the LMM and RM-ASCA+ analyses will guide follow-up analyses using additional machine learning models (PLS-DA, t-SNE).

5) Partial Least Squares Discriminant Analysis (PLS-DA)

- Supervised machine learning approach to analyse differences between the conditions. We will provide the model with a response matrix specifying the conditions, and the model will maximize separation between the conditions. The

method works well with small datasets and multiclass scenarios (here: multiple conditions).

- We will use PLS-DA for feature selection/to explore global structures in the data or find variables that are especially important for one time/condition compared to another. The LMM and RM-ASCA+ analyses will guide the selection of conditions/time points for comparison.
- We will perform cross-validation and permutation testing with 1000 repetitions.

6) T-Distributed Stochastic Neighbour Embedding (t-SNE)

- We will use t-SNE in an exploratory analysis to look for clusters of variables by preserving local relationships (pairwise similarities between data points, clusters).

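### SAP step 1 decides batch adjustment by whether the data look normal, which does not show a batch shift; batch noise can stay in the exercise contrasts wherever a woman's samples span batches

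*SAP*

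**What the plan says.** SAP step 1 (Data preparation) treats batch adjustment, imputation and log transformation together. It opens with "If needed, the outcome data will be batch adjusted, imputed" and goes on to log transformation. The criterion follows: "Adjustments and transformations will depend on whether the data is already normally distributed, and if it is required for the method in question". No batch diagnostic, correction method or plate layout is given in the SAP, and the protocol's assay sections give no layout either.

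One exception is stated: "The metabolomics data from Metabolon already comes in a log-transformed, batch-normalized version". Of these data the SAP says "These will be used in all analyses". The sentence names metabolomics; it does not say whether the Metabolon lipid panel is delivered in the same way.

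Step 2 plans PCA: "We will use PCA to detect outliers and identify global structures/important features". Batch is not mentioned there, and nothing sends a PCA finding back to step 1. The models in steps 3 and 4 (Eqs. 1 and 3) contain time, time-by-condition and a participant intercept. Eq. 2 adds sequence terms. None has a term for batch, plate or run.

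**The concern.** A shift between plates is a difference in location between groups of samples. Added to normal data it often leaves the pooled distribution close to normal. The pooled shape also depends on differences between women, which the participant intercept removes anyway. An analyst who follows the rule can therefore leave a real shift in a normal-looking variable and adjust another variable for an unrelated reason.

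The crossover relies on within-woman contrasts. A shift common to all of a woman's samples drops out of them. A shift that differs between her samples does not, and it adds noise to the comparisons of exercise with rest. What is at stake is precision in NMR, cytokines, hormones and miRNA, in a study whose protocol requires only 20 women with complete data.

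**Working it through.** The documents give no power, effect size, SD or batch figure, so there is no figure of the plan's to reproduce. What follows is an illustration.

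**Inputs from the documents**
- Women: at least 20 with complete data (protocol, Participants); "Up to N=30 women with" BMI above 25 (SAP, Overview).
- Samples per woman: 3 conditions × 4 time points = 12, so 240 samples for 20 women and 360 for 30.
- Threshold: 0.05 divided by the number of principal components (PCs) explaining 95% of baseline variation (SAP step 3).

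**Assumptions**
- Within-woman SD 1; batch SD b = 0, 0.5 or 1.0; four batches; samples spread over them at random.
- True effect 1.4 within-woman SD.
- 59 PCs. This is the ceiling for 20 women: 20 × 3 = 60 baseline samples, less 1 for centring.

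**Step 1. Does normality track batch?** Normal data were simulated for 20 women × 12 samples (between-woman SD 1, random spread, 1,000 data sets per setting), with Shapiro-Wilk at 5%. The SAP names no test; this one is an illustrative choice. Rejection rates were 14% with no batch shift, 12% with b = 0.5 and 16% with b = 1.0. The check hardly responds to the quantity it is meant to decide.

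**Step 2. Effect on the contrast SE.** Take one contrast, such as C3-C1 at T2. Two randomly placed samples fall in different batches with probability about 1 - 1/4 = 0.75, so

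SE = √[2(1 + 0.75b²)/N].

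With N = 20:

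| b | SE | Multiplier |
|---|---|---|
| 0 | √(2/20) = 0.316 | 1 |
| 0.5 | √(2 × 1.1875/20) = 0.345 | √1.1875 = 1.09 |
| 1.0 | √(2 × 1.75/20) = 0.418 | √1.75 = 1.32 |

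A simulation of this layout (20,000 runs) gave multipliers of 1.09 and 1.32. With three batches the factor 0.75 becomes 0.667 and the multipliers are 1.08 and 1.29; with five it becomes 0.8 and they are 1.10 and 1.34.

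**Step 3. Power**, as Φ(1.4/SE - z). For two-sided 0.05/59, z = 3.337.
- b = 0: 1.4/0.3162 = 4.427; Φ(1.090) = 86%.
- b = 0.5: 1.4/0.3446 = 4.063; Φ(0.726) = 77%.
- b = 1.0: 1.4/0.4183 = 3.347; Φ(0.010) = 50%.

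**Step 4. Sensitivity.** The SAP lists five hormones, so that group has at most five PCs. At 0.05/5 (z = 2.576) and N = 20, power is 97%, 93% and 78%. With 30 women, keeping 0.05/59 for comparison, the SEs are 0.258, 0.281 and 0.342, and power is 98%, 95% and 78%.

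**Step 5. Layout.** Eq. 1 was simulated with no true effect (1,500 runs per setting, between-woman SD 1, nominal 5% level). Each cell gives the SD of the contrast for b = 0.5 and 1.0.

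| Layout | N = 20 (0.316 without batch) | N = 30 (0.258 without batch) | Type I error |
|---|---|---|---|
| One batch per woman | 0.312, 0.318 | 0.262, 0.258 | about 0.05 |
| Spread at random | 0.331, 0.420 | 0.283, 0.346 | 0.04 to 0.06 |
| One batch per visit | 0.361, 0.451 | 0.293, 0.363 | 0.06 to 0.07 |

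One batch per woman removes the problem. Random spread costs precision but does not produce false positives.

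**The case against.** The strongest reply is that this is loose drafting rather than a wrong rule. The text begins with a general condition of need and adds a second criterion, whether the method requires the step. Normality is a reasonable consideration for the log step and plainly was not meant to govern imputation. That much stands: normality is not the sole stated trigger, and the criticism bites on batch adjustment. But need is not defined, and whether batch adjustment is called for depends on the assay layout rather than on the statistical method. Neither phrase supplies a batch criterion.

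Three stronger readings are tempting and are not supported.
- **Every exercise contrast is widened.** This holds only where a woman's samples span batches. The layout is unstated, and silence is not evidence of a bad one.
- **The SE multipliers are 1.12 and 1.41.** These come from √(1 + b²), which gives each sample its own independent batch. With four batches some pairs share one, so those values are upper bounds.
- **The exercise effects will be biased or false positives inflated.** If each condition were run as its own batch, simulated type I error reached 0.42 to 0.74. Nothing in the documents suggests that layout.

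It is also fair to say that the study is exploratory and that the SDs, the effect size and the 59 PCs come from no document. The sizes are therefore illustrative; the logical fault in the rule does not depend on them.

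**Conclusion.** The concern holds in limited form. SAP step 1 gives no valid basis for deciding batch adjustment, and neither the models nor the PCA step makes up for this. It applies to NMR, cytokines, hormones and miRNA, and to the Metabolon lipid panel unless that is confirmed to arrive batch-normalised. The Metabolon metabolomics data are not affected.

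The consequence is conditional: lost precision where a woman's samples span batches, and none where they share one. How much is lost depends on the assumed batch SD, the number of PCs and the number of women. It runs from a few percentage points of power for a small panel with modest batch noise to more than a third of them in the worst case shown (86% to 50%). This should be corrected, and the correction is cheap. Confidence in the size is moderate because the layout and the assay variances are unknown.

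**What to change.** Replace the sentence in step 1 with separate rules for batch and for transformation.

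1. **Batch.** For every outcome group assayed in more than one batch and not already batch-normalised, include a batch term in Eqs. 1 and 3, or use a correction that preserves time and condition, whatever the distribution. State whether the Metabolon lipid panel is already normalised.
2. **Layout.** For assays not yet run, place all 12 samples of a woman in one batch, in random position. For assays already run, report the layout.
3. **Transformation.** Decide it from the Eq. 1 residuals, not from the pooled raw data, and do not log again any data delivered on a log scale.

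The cost is SAP wording, a few degrees of freedom for batch and a plate map. On a 96-well format with about 88 usable wells (an assumption), a plate holds seven women (7 × 12 = 84). Twenty women then need 3 plates and thirty need 5, the same as without the restriction (240/88 and 360/88, rounded up). The one-batch layout was checked by simulation; the batch term was not, and is recommended on general grounds.
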